## 2 STUDY OBJECTIVES

### 2.1 Primary Objective

The primary objective is to demonstrate the efficacy of *Octafibrin* for on-demand treatment of acute bleeding episodes (spontaneous or after trauma).

### 2.2 Secondary Objectives

The secondary objectives are:

- To determine the single-dose pharmacokinetics of *Octafibrin* in paediatric subjects with congenital fibrinogen deficiency
- To investigate an association between the overall clinical assessment of haemostatic efficacy and the surrogate endpoint ‘clot strength’ or ‘clot firmness’ (referred to as ‘maximum clot firmness’ [MCF] in this protocol) that was used as a surrogate endpoint for haemostatic efficacy and determined via thromboelastometry (ROTEM) in the pivotal PK study FORMA-01. Therefore, MCF as surrogate efficacy parameter will be determined before and after the first infusion of IMP for treatment of a bleeding episode.
- To achieve a peak target plasma fibrinogen level of 100 mg/dL in minor bleeds and 150 mg/dL for major bleeds 1 hour post-infusion
- To determine the response to *Octafibrin* based on incremental in vivo recovery (IVR)
- To demonstrate the efficacy of *Octafibrin* in preventing bleeding during and after surgery
- To assess the safety of *Octafibrin* in subjects with congenital fibrinogen deficiency, including immunogenicity, thromboembolic complications, and early signs of allergic or hypersensitivity reactions

### 3 INVESTIGATIONAL PLAN

#### 3.1 Primary and Secondary Endpoints

##### 3.1.1 Primary Endpoint

The primary endpoint is the **overall clinical assessment of the haemostatic efficacy of Octafibrin** in treating the first documented bleeding episode of each patient.

The first bleeding episode covers the time period from the first *Octafibrin* infusion for the treatment of a bleeding episode until 24 hours (i.e., 1 day) after the last infusion or the end of the treatment observation period, whichever comes last.

The investigator's overall clinical assessment of haemostatic efficacy for bleeding will be based on a 4-point haemostatic efficacy scale as described in Section 7.2.1. The final efficacy assessment of each patient will be adjudicated by the Independent Data Monitoring & Endpoint Adjudication Committee (IDMEAC).

In the final analysis, the number of subjects per outcome category will be assessed.

##### 3.1.2 Secondary Endpoints

###### 3.1.2.1 Secondary PK Endpoints

The following PK parameters will be assessed as secondary endpoints:

- Area under the concentration-time curve (AUC)
- Response: Incremental In Vivo Recovery (IVR)
- Classical IVR
- Terminal elimination half-life ( $t_{1/2}$ )
- Maximum plasma concentration ( $C_{max}$ )
- Time to reach maximum plasma concentration ( $T_{max}$ )
- Mean residence time (MRT)
- Volume of distribution ( $V_{ss}$ )
- Clearance (Cl)

###### 3.1.2.2 Secondary Efficacy Endpoints

The following efficacy parameters will be calculated as secondary endpoints:

- MCF assessment before first infusion and 1 hour after end of first infusion of each documented bleeding episode (see Section 7.2.2.2)
- Fibrinogen plasma level before and 1 hour after the end of each subsequent infusion as well as at the time of the overall clinical assessment of haemostatic efficacy (i.e., 24 hours after the last infusion or end of the observation period of each documented bleeding episode)

- Response after the first infusion of each bleeding episode as indicated by incremental IVR, calculated as the maximum increase in plasma fibrinogen (Clauss data) between the pre-infusion and the 3-hour post-infusion measurement, divided by the exact dose of *Octafibrin* (expressed as mg/kg dosed) (see Section 7.2.2.3)
- Efficacy of *Octafibrin* in all bleeding episodes collected in the study using the investigator's overall clinical assessment of haemostatic efficacy for bleeding based on a 4-point haemostatic efficacy scale
- Efficacy of *Octafibrin* in preventing bleeding during and after surgery as assessed at the end of surgery by the surgeon and post-operatively by the haematologist using two 4-point haemostatic efficacy scales (see Section 7.2.2.4). An overall efficacy assessment taking both the intra- and post-operative assessment into account will be adjudicated by the IDMEAC. The surgical observation period starts with the first dose of *Octafibrin* administered prior to elective surgery (Day 1) and, depending on the severity of the event, will last at least 3 post-operative days for minor and 7 post-operative days for major surgeries or until the day of the last post-operative infusion, whichever comes last. The number of subjects per outcome category will be assessed and will include at least 4 surgeries.

### **3.1.2.3 Safety Endpoints**

The following safety parameters will be calculated as secondary safety endpoints:

- Vital signs
- Physical examination
- Thromboembolic event (TEE) questionnaire
- Routine clinical laboratory assessment, including coagulation parameters
- Adverse events (AEs), including thromboembolic complications and early signs of allergic or hypersensitivity reactions
- Thrombogenicity testing before and after each IMP infusion for the treatment of bleeding, except on the Day of Last Infusion
- Immunogenicity testing before the first infusion of IMP and on Day 30 after the treatment of each bleeding episode

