# To be re-reviewed if period between screening and treatment is more than 3 months.

[a] If, based on the daily assessment, the investigator considers an additional infusion of *Octafibrin* necessary (see footnote f).

[b] Within 30 minutes before infusion.

[c] Measured in local laboratories.

[d] Measured in the central laboratory.

[e] Serum retention sample for potential viral testing.

[f] If the *Octafibrin* infusion administered on this day is deemed the only infusion needed for treatment of the subject's bleeding event, the post-infusion assessments as detailed in the more comprehensive schedule for the Day of Last Infusion must be performed.

[g] If the actual fibrinogen plasma level is below the accepted lower limit of the target fibrinogen plasma level, the subject **should** receive another infusion of *Octafibrin*. If the fibrinogen plasma level is greater than or equal to the accepted lower limit of the target fibrinogen plasma level, *Octafibrin* **should not** be administered.

[h] Including thromboembolic events or hypersensitivity reactions.

[i] Haematology only.

[j] Retention serum sample taken before PK infusion; PK infusion of 70 mg/kg of *Octafibrin*; subsequent blood sampling (see separate PK flow chart) (if not previously performed prior to a surgical procedure).

FLOW CHART OF ASSESSMENTS FOR SURGICAL PROPHYLAXIS

Screening	SURGICAL OBSERVATION PERIOD											Study Completion Visit
	Before surgery		Day 1 Surgery			Any POP day (i.e., up to and excluding either Day 4 for minor and Day 8 for major surgery or the day of the last post-operative infusion, whichever comes later)			Last POP Day (i.e., either Day 4 for minor and Day 8 for major surgery or the day of the last post-operative infusion, whichever comes later)			
	Within 12 h before start	Within 3 h before start	Start	Intra-operative	End	Daily [i]	Pre-infusion	1 h post-infusion (± 15 min)	Daily [i]	Pre-infusion	1 h post-infusion (± 15 min)	
Eligibility and informed consent	x	#										
Demography	x											
Medical history, review of previous therapy	x											
Details of surgery (location, type, severity)	x											
Estimated blood loss, duration of surgery, transfusion requirements	x											
Any planned ancillary therapy during the surgery (e.g., antifibrinolytics)	x											
Actual duration of surgery			x									
Details of hospitalisation and follow-up (narrative)			x									
Actual blood loss and transfusion requirements			x									

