# To be re-reviewed if period between screening and treatment is more than 3 months.

[a] ≤30 minutes before and after each infusion of Octafibrin.

[b] Measured in local laboratories.

[c] Measured in central laboratory.

[d] Plasma retain sample for potential retesting; serum retain sample for potential viral testing.

[e] If the actual fibrinogen plasma level is below the accepted lower limit of the target fibrinogen plasma level, the subject **should** receive another infusion of Octafibrin. If the fibrinogen level is greater than or equal to the accepted lower limit of the target fibrinogen level, Octafibrin **should not** be administered.

[f] Intraoperative efficacy assessment by surgeon.

[g] Postoperative efficacy assessment by haematologist.

[h] Including thromboembolic events and hypersensitivity reactions.

[i] Only if no infusions given.

[j] Retention serum sample taken before PK infusion; PK infusion of 70 mg/kg of Octafibrin; subsequent blood sampling (see separate PK flow chart) (if not previously performed prior to a bleeding episode).

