## **3.2 Overall Study Design and Plan**

This is a multinational, multi-centre, prospective, open-label, uncontrolled, Phase III study to assess the efficacy, safety, and pharmacokinetics of *Octafibrin* for on-demand treatment of acute bleeding and surgical prophylaxis in paediatric subjects with congenital fibrinogen deficiency.

At least 12 male or female paediatric subjects with congenital fibrinogen deficiency will be enrolled into the study and undergo PK assessment. Of these 12 subjects, at least 6 subjects will undergo on-demand treatment of 6 first bleeding episodes. Of these 6 subjects, at least 3 should be aged between 0 and <6 years and 3 should be aged between 6 and <12 years. In addition, at least 2 surgical procedures will be assessed. The study will be conducted in approximately 5 study centres worldwide.

During the study observation period, enrolled patients will participate in a 14-day PK phase with administration of a single dose of *Octafibrin* and will subsequently be treated for any bleeding episodes or planned surgeries that can be managed under the protocol. Patients may remain in the study until at least 12 patients have undergone PK assessment, the 6th patient (at least 3 patients each in the specified age groups) has at least one documented bleeding episode, and a minimum of 2 surgical procedures have been performed.

The study will be considered completed when a minimum of 12 subjects have undergone PK assessment, 6 subjects (at least 3 subjects aged between 0 and <6 years and 3 subjects aged between 6 and <12 years) have at least one documented bleeding episode, and at least 2 surgical procedures have been documented. The study as a whole should be completed within 5 years.

As many bleeding episodes or surgeries as possible occurring throughout the study observation period will be documented. Only the first bleeding episodes will be used for the analysis of the primary endpoint. All bleeding episodes documented in the study will be assessed as a secondary endpoint.

The investigator will inform the monitor of any recruitment difficulty or delay of the anticipated completion date.

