### 6.2.2 Planned Duration for an Individual Subject

All patients will undergo a PK study after screening. This will have a duration of 14 days, after which a patient can be treated for a bleeding episode or planned surgical procedure when they occur.

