### 9.2 Populations for Analysis

#### 9.2.1 Safety Population

The safety population will include all subjects who received at least one infusion of the IMP. The analysis of safety will be based on this population.

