## 9.4 Safety Analysis Plan

The analysis of safety will be based on the safety population.

All AEs (including events likely to be related to the underlying disease, or a concomitant illness or medication or clinically significant abnormalities in laboratory parameters or vital signs) will be displayed in summary tables and listings.

Incidence of AEs will be given as numbers and percentages of subjects with:

- Any AE
- Any SAE
- Any AE probably or possibly related to the IMP
- Any AE temporally related (within 24 hours after end of infusion) to the IMP
- Any severe AE
- Any withdrawal due to AE
- Any AE by Medical Dictionary for Regulatory Activities (MedDRA) preferred term (descending frequency)
- Any AE temporally related (within 24 hours after end of infusion) by MedDRA preferred term (descending frequency)
- Any AE by MedDRA system organ class (SOC)
- Any AE temporally related (within 24 hours after end of infusion) by MedDRA SOC

Summary tables for AEs will be given by SOC and preferred term. Additionally, AEs will be summarised by severity and relationship to the IMP

The MedDRA coded terms and the corresponding original (verbatim) terms used by the investigator will be listed.

For laboratory variables (analyses of haematology, clinical chemistry, and thrombogenicity), the mean, standard deviation, median, and range will be presented per time point. Laboratory variables will also be presented graphically. Intra-individual changes between pre-infusion and the respective post-infusion time points will be analysed using shift tables and graphical presentations. Fibrinogen inhibitor testing data will be summarized in frequency tables.

For vital signs, the mean, standard deviation, median, and range will be presented per time point (original values and intra-individual changes between pre-infusion and the respective post-infusion time points). Physical examination data will be presented in frequency tables.

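### Inhibitor testing is promised before the first infusion but scheduled only around bleeds, so it follows the PK dose and leaves exposed children without a bleed with no scheduled assay

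*Protocol*

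**What the plan says.** **Aim and population.** The safety objective in Protocol 2.2 covers subjects with congenital fibrinogen deficiency, "including immunogenicity, thromboembolic complications, and early signs of allergic or hypersensitivity reactions". Under Protocol 9.2.1, "The safety population will include all subjects who received at least one infusion of the IMP". Protocol 9.4 states: "Fibrinogen inhibitor testing data will be summarized in frequency tables", and SAP 12 says the same.

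**Endpoint.** Protocol 3.1.2.3 gives it as "Immunogenicity testing before the first infusion of IMP and on Day 30 after the treatment of each bleeding episode"; the Study Outline and SAP 4.3.7 carry the same text.

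**Order of exposure.** Protocol 6.2.2: "All patients will undergo a PK study after screening". Bleeds and surgery are treated after that 14-day phase. Protocol 3.2 agrees: after the single PK dose, patients "will subsequently be treated for any bleeding episodes or planned surgeries that can be managed under the protocol".

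**Laboratory.** Table 5 in Protocol 7.3 specifies fibrinogen inhibitor testing on citrated plasma in the central laboratory. Leftover serum and plasma are stored and may be tested further if the need arises.

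**SAP outputs.** The list in SAP 14 has no inhibitor frequency table. Listing 16.2.8.2 covers inhibitor results at baseline and during the study for all subjects, but in factor IX terms. SAP 4.3.7 and 5.4 also refer to factor IX inhibitors.

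**The concern.** Read literally, the endpoint promises a sample from before any exposure to the product. The schedules tie the assay to bleeds, and a bleed normally comes after the PK dose. Two things are at stake.

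First, a positive result on bleed Day 1 would be hard to classify as pre-existing or as arising after the PK dose. A baseline not sampled before exposure cannot be drawn later.

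Second, the safety population includes every infused child, but a child with no treated bleed contributes nothing scheduled to the inhibitor summary. SAP 7.1 requires both N and n in each display, so the shortfall would be visible but not repaired.

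**Working it through.** The plan has no figure of its own to reproduce: Protocol 9.1 gives no sample size calculation. The check compares schedules and then counts.

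**Step 1. Where the assay is listed**

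| Contact | Protocol source | Inhibitor sample |
|---|---|---|
| Screening | 6.1.1 | none |
| PK phase, pre-infusion to PK-Day 14 | 6.1.2, PK flow chart | none (fibrinogen and retention serum only) |
| Bleed Day 1, pre-infusion | 6.1.3.1, bleeding flow chart | yes |
| Bleed Day 30 | 6.1.3.4, bleeding flow chart | yes |
| Surgery, pre-operative to Last Post-Operative Day | 6.1.4.1 to 6.1.4.3, surgery flow chart | none |
| Study Completion Visit | 6.1.5 | none (no blood draw listed) |

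**Step 2. What each path yields**

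- PK, then bleed: Day 1 (already exposed) and Day 30.
- PK only, or PK then surgery: nothing scheduled.
- Bleed first, if allowed (Protocol 3.2.2 describes inclusion at presentation with a bleed): Day 1 is pre-exposure.
- Surgery first, if allowed (6.1.4.1 calls surgery Day 1 the day of the first dose): still nothing, because the pre-operative list has no inhibitor sample.

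**Step 3. Counts.** Inputs from Protocol 3.2: at least 12 children with PK, of whom at least 6 have a treated bleed.

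- No scheduled assay = exposed − with a bleed = 12 − 6 = 6, or 6/12 = 50%, at exactly the minimum. If all 12 bleed it is 0.
- Protocol 4.5.2 replaces children without a documented bleed. If 15 or 18 were exposed to reach 6 with a bleed (assumed totals), the count is 15 − 6 = 9 (60%) or 18 − 6 = 12 (67%).
- Scheduled pre-exposure assay at the minimum: 0 of 12 under PK-first; at most 6 of 12 if all six children with a bleed entered through it.

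**Step 4. Precision, for scale.** With no positives among n children, the exact two-sided 95% upper limit is 1 − 0.025^(1/n).

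- n = 6: 45.9%.
- n = 12: 26.5%.

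The n = 12 figure suits a common pre-PK baseline. After exposure, PK-Day 14 (312 h / 24 = 13 days after the infusion) and bleed Day 30 (29 days after the first infusion for that bleed) are different time points and should not be pooled into one n of 12.

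**Step 5. Separate minor point, AEs after surgery.** Protocol 3.2.3 and 7.4.1.2 limit AE recording to the surgical observation period. Under 6.1.4.3 that period can end on the day of the last infusion. Protocol 9.4 and SAP 12 tabulate AEs within 24 hours after the end of an infusion. If recording closes at midnight (an assumption), a last infusion ending at 08:00, 12:00 or 16:00 leaves 8, 12 or 16 of the 24 hours unrecorded.

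**The case against.** **The endpoint may mean the first infusion of each bleed.** The schedule then delivers it in full, and testing other children is an added request. This reading is fair and the text allows it. The objective in Protocol 2.2 would still have no scheduled data for exposed children without a bleed, and SAP listing 16.2.8.2 suggests that a baseline result was expected for all.

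**Most children may bleed.** Eligibility requires an expected bleed or planned surgery, Protocol 1.1 describes frequent severe bleeding in afibrinogenaemia, and the study may run 5 years. This stands: 6 of 12 is the count at exactly the minimum, not a forecast.

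**Other evidence exists.** Central activity and antigen are measured before the PK dose and at seven later times. Exclusion criterion 8 removes children with a known or suspected inhibitor, and leftover plasma may be tested. All of this helps, but indirectly. Recovery data are not an inhibitor assay, criterion 8 does not rest on a study test, the dedicated pre-PK retention sample is serum whereas the assay needs citrated plasma, and testing leftovers is optional.

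**PK-first is not uniform.** Protocol 3.2.2 and 6.1.4.1 suggest other orders. Footnotes [j] of the flow charts ("if not previously performed prior to a surgical procedure" and "if not previously performed prior to a bleeding episode") seem to support PK-first, but no cell in the available text carries that mark, so I place no weight on them. The claim is conditional on 3.2 and 6.2.2.

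**Limits of 45.9% and 26.5% are both wide in a descriptive study.** True. They show scale only; the case rests on the missing baseline and the untested children.

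**Conclusion.** The conflict between endpoint and schedule is real and should be corrected. Under the PK-first rule no child has a scheduled pre-exposure inhibitor result, and exposed children without a treated bleed have no scheduled result at all: 6 of 12 at exactly the planned minimum, anywhere from 0 upward depending on how many bleed and how many are replaced.

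A reader might infer that half of the children will go untested, or that no pre-exposure result can exist. The documents support neither. The number of children who bleed is not capped at 6, a child entering through a bleed would have a pre-exposure Day 1 sample, and stored plasma could be assayed. The gap is in scheduled testing, not in the possibility of testing.

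A reader might also extend the AE point to the whole study. It does not reach bleeds, where AEs are recorded to Day 30. It concerns only surgery in which the last infusion falls on the Last Post-Operative Day, and non-serious events. SAEs are collected throughout participation, and the note to Table 5 documents thromboembolic events to Day 30. With a minimum of 2 procedures, it is minor.

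**What to change.** 1. Add the central inhibitor assay on citrated plasma at the existing pre-PK draw, and define that result in the SAP as the inhibitor baseline.
2. For children without a bleed, add one post-exposure assay. PK-Day 14 uses an existing draw; a later sample, such as at the Study Completion Visit, is preferable. Protocol 7.3.4 mentions a retention sample at that visit while 6.1.5 lists no draw, so the two must be reconciled. Report these results separately from bleed Day 30 results.
3. Replace the factor IX wording in SAP 4.3.7, SAP 5.4 and listing 16.2.8.2 with fibrinogen, and add the promised inhibitor frequency table to SAP 14.
4. Reconcile Protocol 3.2.2 and 6.1.4.1 (and the matching Study Outline text on surgery Day 1) with 3.2 and 6.2.2 on whether PK always comes first.
5. Separately, record all AEs until 24 hours after the end of the last surgical infusion, or report how many subjects had an incomplete window.

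**Cost.** A protocol amendment and a SAP edit. At 12 children, 12 baseline assays plus 0 to 12 post-exposure assays: 12 if every child bleeds and none is tested on PK-Day 14, 12 + 6 = 18 if only six children without a bleed are tested, 12 + 12 = 24 if all are tested on PK-Day 14. Some extra plasma is needed. The documents do not give the volume, which matters because eligibility starts at age 0. A completion-visit sample may mean one more draw, and the AE change one contact per surgery.

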## **3.2 Overall Study Design and Plan**

This is a multinational, multi-centre, prospective, open-label, uncontrolled, Phase III study to assess the efficacy, safety, and pharmacokinetics of *Octafibrin* for on-demand treatment of acute bleeding and surgical prophylaxis in paediatric subjects with congenital fibrinogen deficiency.

At least 12 male or female paediatric subjects with congenital fibrinogen deficiency will be enrolled into the study and undergo PK assessment. Of these 12 subjects, at least 6 subjects will undergo on-demand treatment of 6 first bleeding episodes. Of these 6 subjects, at least 3 should be aged between 0 and <6 years and 3 should be aged between 6 and <12 years. In addition, at least 2 surgical procedures will be assessed. The study will be conducted in approximately 5 study centres worldwide.

During the study observation period, enrolled patients will participate in a 14-day PK phase with administration of a single dose of *Octafibrin* and will subsequently be treated for any bleeding episodes or planned surgeries that can be managed under the protocol. Patients may remain in the study until at least 12 patients have undergone PK assessment, the 6th patient (at least 3 patients each in the specified age groups) has at least one documented bleeding episode, and a minimum of 2 surgical procedures have been performed.

The study will be considered completed when a minimum of 12 subjects have undergone PK assessment, 6 subjects (at least 3 subjects aged between 0 and <6 years and 3 subjects aged between 6 and <12 years) have at least one documented bleeding episode, and at least 2 surgical procedures have been documented. The study as a whole should be completed within 5 years.

As many bleeding episodes or surgeries as possible occurring throughout the study observation period will be documented. Only the first bleeding episodes will be used for the analysis of the primary endpoint. All bleeding episodes documented in the study will be assessed as a secondary endpoint.

The investigator will inform the monitor of any recruitment difficulty or delay of the anticipated completion date.

Patients should be treated with the investigational medicinal product (IMP) whenever possible. If, in the opinion of the investigator, a bleeding episode is not effectively stopped or surgical prophylaxis is not adequate after the recommended dose of *Octafibrin* has been administered, the subject may receive a different licensed fibrinogen concentrate (e.g., Haemocomplettan P®/RiaSTAP™) or whatever the investigator considers standard of care. The use of another licensed fibrinogen concentrate is also permitted in emergency situations, e.g., if the IMP is not available for the patient in time.

